**Complete Response/unconfirmed (CRu)**

A residual lymph node mass greater than 1.5 cm in greatest transverse diameter that has regressed by more than 75% in the SPD. Individual nodes that were previously confluent must have regressed by more than 75% in their SPD compared with the size of the original mass.

**Partial Response (PR)**

$\geq 50\%$  decrease in SPD of the six largest dominant nodes or nodal masses. These nodes or masses should be selected according to the following features: (a) they should be clearly measurable in at least two perpendicular dimensions, (b) they should be from as disparate regions of the body as possible, and (c) they should include mediastinal and retroperitoneal areas of disease whenever these sites are involved.

**Stable Disease (SD)**

Stable disease is defined as less than a PR but is not progressive disease

**Progressive Disease (PD)**

- $\geq 50\%$  increase from nadir in the SPD of any previously identified abnormal node for PRs or non-responders.
- Appearance of any new lesion during or at the end of therapy.

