### 8.1.1 Procedures

Medical history (incl. of B-symptoms)
Current medication
Clinical examination (including palpation of lymph node regions)
Shipping of the biopsy tissue to a reference pathologist of the GLSG
Laboratory testing:
- Differential blood cell count (hemoglobin, leucocytes, thrombocytes, neutrophils, lymphocytes)
- Clinical chemistry (sodium, potassium, AST/ALT, total bilirubin, alkaline phosphatase, creatinine)
- LDH
- albumin, immunoglobulins, immunefixation
- $\beta_2$ microglobuline
- Peripheral blood (10 ml EDTA) for MRD analysis and STRECK tube (10 ml) for cell-free DNA collection
- Hepatitis- und HIV – serology (not applicable if there are values < 3 months )
- Pregnancy test (serum) for all women with childbearing potential (including tubal ligation)
CT or MRI (<= 4 months), if necessary: additional ultrasound
- head&neck*
- thorax*
- abdomen*
- pelvis including inguinal region*

\*These regions must be screened using 3D sectional imaging and should also be scanned during the follow-up examinations from months 6 on. Ultrasound can be used additionally, but it cannot replace a CT or MRI since the morphological remission criteria are based on 3D sectional imaging. A FDG-PET/CT of these regions can be used instead of CT or MRI.

Site-specific examinations:

Thyroid testing in case of cervical or supraclavicular lymphoma (TSH, fT3/fT4)
Consultation of a head&neck in case of supra-diaphragmal lymphoma

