8.1.4 Examinations during therapy (up to week 18)– **before each Gazyvaro administration:**

Differential blood cell count (hemoglobin, leucocytes, thrombocytes, neutrophils, lymphocytes)
Assessment of AEs
Pregnancy test (serum or urine) in premenopausal female patients before Gazyvaro administration in week 1, week 4, week 8, week 12 and week 16. In case of a positive urine pregnancy test, dosing will be delayed, until patient's status is determined by a serum pregnancy test

– **week 7:**

CT imaging of the involved lymphoma region for radiation planning and response assessment
Palpation of the lymphatic region
Laboratory testing:
- Differential blood cell count (hemoglobin, leucocytes, thrombocytes, neutrophils, lymphocytes)
- clinical chemistry (sodium, potassium, AST/ALT, total bilirubin, alkaline phosphatase, creatinine)

- LDH
Assessment of AEs

- week 18

Medical history
Clinical examination (including palpation of lymph node regions, skin reaction in the radiation area)
ECOG-Performance status
Laboratory testing:
- Differential blood cell count (hemoglobin, leucocytes, thrombocytes, neutrophils, lymphocytes)
- clinical chemistry (sodium, potassium, AST/ALT, total bilirubin, alkaline phosphatase, creatinine)
- LDH
EORTC QLQ-C30, FACT-Lym questionnaires
In dependence of the initial FDG-PET/CT before the first Gazyvaro administration: 
 
• FDG-PET/CT of the initially involved region for response evaluation (central review) for patients with initially PET positive remaining lymphoma
 
• Contrast enhanced CT/MRI for patients with initially PET negative remaining lymphoma
 
• No imaging for patients without initially remaining macroscopic lymphoma after surgical intervention for proof of histology
 

Peripheral blood (10 ml EDTA) for MRD analysis and STRECK tube (10 ml) for cell-free DNA collection
Assessment of AEs

8.1.5 Follow-up examinations month 6, 12, 18, 24

Medical history (incl. assessment of B-symptoms)
Clinical examination (including palpation of lymph node regions, skin reaction in the radiation area)
ECOG-Performance status
Laboratory testing:
- Differential blood cell count (hemoglobin, leucocytes, thrombocytes, neutrophils, lymphocytes)
- Clinical chemistry (sodium, potassium, calcium, AST/ALT, total bilirubin, alkaline phosphatase, creatinine)
- LDH
- Total protein, protein-electrophoresis
CT or MRI (<= 4 months), if necessary: additional ultrasound

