**Metabolic Treatment Failure / Metabolic Progressive Disease (MPD)**

An increase in FDG uptake to a score of 5, score 5 with no decrease in uptake, and new FDG-avid foci consistent with lymphoma

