**8.3.2 Criteria of Remission of CT/MRI**

The morphologic remission is according to the NCI criteria [63].

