**Complete Response (CR)**

All lymph nodes and nodal masses must have regressed to normal size ( $\leq 1.5$  cm in their greatest transverse diameter for nodes  $\geq 1.5$  cm before therapy). Previously involved nodes that were 1.1 to 1.5 cm in their greatest transverse diameter before treatment must have decreased to  $\leq 1$  cm in their greatest transverse diameter after treatment, or by more than 75% in the sum of the products of the greatest diameters (SPD).

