### 11.6 Definition of Target Variables

Progression-free survival:

- a) Calculated from start of therapy up to the time of progression (morphologic or metabolic) or death
- b) Calculated from start of therapy up to the time of progression (morphologic or metabolic) or death in patients with initially remaining lymphoma (morphologic or metabolic)

Overall survival:

Calculated from start of therapy up to the time of death

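### As printed, morphologic progression omits new lesions after therapy and regrowth after CR/CRu, and PFS does not name relapse, so 2-year PFS can only err upward if the text is applied literally

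*Combined protocol and SAP*

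**What the plan says.** Section 8.3.2 prints two routes to morphologic progressive disease. One is an SPD rise of at least 50%, described as an "increase from nadir in the SPD of any previously identified abnormal node for PRs or non-responders". The other is "Appearance of any new lesion during or at the end of therapy". The section refers to the NCI criteria (reference 63) but prints no relapse category, and no rule for nodes that regrow after CR or CRu.

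Section 11.6 a) defines PFS as "Calculated from start of therapy up to the time of progression (morphologic or metabolic) or death". Part b) is the same for patients with initially remaining lymphoma. The metabolic route in section 8.3.1 includes "new FDG-avid foci consistent with lymphoma", with no time limit.

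The Study Schedule ends antibody treatment in week 16 and salvage irradiation, where given, in week 23/24. CT/MRI follows at months 6, 12, 18, 24 and 30. The only scheduled response PET is in week 18, in patients who were PET positive at the start. For the listed body regions, including in follow-up, section 8.1.1 allows a substitute: "A FDG-PET/CT of these regions can be used instead of CT or MRI".

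Sections 2.3 and 11.2 list PFS at 2 years and, separately, the relapse rate and pattern of recurrence at all follow-up visits. Relapse is not defined.

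**The concern.** Both printed routes to morphologic progression carry a limit: the first by response category, the second by time. The scans at months 12, 18 and 24 come after therapy in every patient; month 6 is arguable for patients who had salvage irradiation. On the literal text, two findings on those scans are not progression: a new lesion, and regrowth of a node that had reached CR or CRu. PFS does not name relapse, so the patient stays event-free.

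Patients whose lymphoma was completely removed at biopsy are the clearest case. They have no abnormal node to follow, and section 8.1.4 prescribes no week-18 imaging "for patients without initially remaining macroscopic lymphoma after surgical intervention for proof of histology". The time-limited new-lesion rule is their only CT/MRI route to progression.

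Late in-field recurrence is the residual risk that section 1.3 accepts in exchange for the lower radiation dose, and section 1.1.1 reports that most recurrences in the earlier randomized radiotherapy trial lay outside the field. Two-year PFS should register both kinds. Sites may also classify the same finding differently: there are 30 of them, and section 14.2 foresees central review of follow-up CT/MRI only where clarification is needed.

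**Working it through.** **Which events count on the literal text, after the end of therapy**

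| Follow-up finding | PFS event? |
|---|---|
| Death | Yes |
| At least 50% SPD growth from nadir in a partial responder or non-responder | Yes |
| New FDG-avid foci, if PET/CT replaces CT/MRI | Yes |
| New lesion on CT/MRI | No |
| Regrowth on CT/MRI after CR/CRu | No |

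The omissions work in one direction only: an uncounted relapse raises the PFS estimate.

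**The plan's own figures.** Section 11.1 gives no planning figure for PFS. Its figures for the primary endpoint reproduce: 1.96 × √(0.6 × 0.4 / 50) = 13.6 points (stated as about 13.5), and 93 × 0.85 = 79 treated patients. No stated number is in dispute.

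**Illustration of size.** Inputs:
- n = 79 treated patients (section 11.1).
- True 2-year PFS S = 86%, the MIR result in section 1.1.5. That it applies here is an assumption.
- Constant hazard (assumption).
- End of therapy t0 = week 16 or week 24, that is 3.68 or 5.52 months at 4.348 weeks per month.
- c = share of late events that still count. The documents do not give it, so it is varied.

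Hazard: h = −ln(0.86)/24 = 0.00628 per month.

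Events by t0: 1 − exp(−h × t0) = 2.29% (week 16) or 3.41% (week 24).

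Late events: (14% − 2.29%) × 79 = 9.3, or (14% − 3.41%) × 79 = 8.4, of 0.14 × 79 = 11.1 in all.

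Apparent PFS = exp(−h × t0) × exp(−c × h × (24 − t0)):

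| c | Apparent PFS, week 16 / week 24 | Overstatement (points) |
|---|---|---|
| 1 | 86.0 / 86.0% | 0 |
| 0.75 | 88.8 / 88.5% | 2.8 / 2.5 |
| 0.5 | 91.7 / 91.1% | 5.7 / 5.1 |
| 0 | 97.7 / 96.6% | 11.7 / 10.6 |

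As a rough check at c = 0.5, losing half of 9.3 or 8.4 events among 79 patients is 5.9 or 5.3 points.

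If the month-6 scan is conceded to be at the end of therapy, t0 = 6 months. Late events are then (0.963 − 0.860) × 79 = 8.1, and the overstatement at c = 0.5 is 5.0 points.

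The row c = 0 is a ceiling, since the first three findings in the first table still count. The ceiling depends on S: 16.6 / 15.0 points at S = 80% and 8.4 / 7.6 at S = 90%.

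For scale, the 95% half-width at 86% with 79 patients and no censoring is 1.96 × √(0.86 × 0.14 / 79) = 7.7 points.

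**The case against.** Five arguments weigh against the point.

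1. Section 8.3.2 adopts published criteria by reference, and these may define relapse. They cannot be checked from the documents. Even if they do, the protocol prints its own progression rule with explicit limits, and section 11.6 does not mention relapse. This argument lowers the likely harm but does not remove the gap.

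2. The intent is fairly clear. Section 11.6 a) applies PFS to all treated patients, including those with no lymphoma left, for whom progression can hardly mean anything but a new lesion. Section 1.1.2 treats the excess recurrences in the FORT trial as inferior PFS. Sections 2.3 and 11.2 use the PD category at month 6. This stands: the two readings are not of equal weight. It is a reason to bring the text into line with the intent.

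3. Relapses would not be hidden. They are a separate secondary endpoint, section 11.4 analyses recurrence rates with Wilson intervals, and section 2.1 asks for the site of recurrence in three subgroups. This also stands. A reader might infer that late failures would vanish from the report; the documents do not support that. What could happen is a PFS figure that disagrees with the relapse rate beside it.

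4. The size rests on an unknown share. This is correct, and the table should be read as a range.

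5. A reader might infer that none of the patients who are PET negative at staging has another CT/MRI route to progression. Section 8.1.4 separately describes PET-negative patients with remaining lymphoma, who do have nodes to follow, so the group cannot be treated as one.

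**Conclusion.** The point holds as a defect of wording with a known direction and an unknown size. Followed exactly as printed, sections 8.3.2 and 11.6 leave new lesions on CT/MRI after therapy, and regrowth after CR/CRu, outside PFS, so 2-year PFS could only be too high.

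With a true 2-year PFS of 86%, a constant hazard and 79 patients, the overstatement runs from 0 points, if all late events are counted in practice, to about 5 to 6 points if half are. A reader might take the ceiling of 10.6 to 11.7 points as an expected bias. The documents do not support that: it requires losing every late event, including deaths, PET-detected foci and regrowth in partial responders and non-responders.

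PFS here is secondary and descriptive, with no hypothesis test attached. The primary endpoint, overall survival, the sample size and the week-18 salvage decision are unaffected. The correction should be made, but the point does not threaten the trial's main result.

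**What to change.** Three changes of wording, carried into the SAP:

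1. In section 11.6 a) and b), define the PFS event as progression or relapse, by morphologic or metabolic criteria, or death.
2. In section 8.3.2, let a new lesion count at any visit, during therapy or follow-up.
3. In section 8.3.2, add the relapse definition for previously involved nodes after CR/CRu from the criteria already cited there. It should agree with the printed CR size limits, which differ by the size of the node before treatment. Use the same definition for the relapse-rate endpoint, so that the two results can be reconciled.

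If relapse was always meant to count, these changes only put that on record. They need no new data, visits or software. Section 11.4 has the SAP finalized before database lock, so the definitions can be fixed by then.

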**8.4 Parameters of safety**

Clinical examination and medical history, blood values at the above mentioned visits. The classification of side effects is according to the NCI-CTC criteria version 4.03

**8.5 Additional Parameters**

The quality of life is assessed on a longitudinal time line using the EORTC QLQ-C30 questionnaire and the FACT-Lym questionnaire.

## 9. FOLLOW-UP AND POSSIBLE TREATMENTS AFTER END OF TRIAL

Follow-up procedures and possible further treatments after the trial (early ending or after month 30) should be performed according to local standard procedures at each site. The results of this extended follow-up should be collected with the consent of the patient as in a register. It is the goal to analyze these long time follow-up data retrospectively in the future.

**In case of a recurrence at the primary involved site after 2x2 Gy, it should be respected, that a "full dose" up to the target dose of the MIR trial (40 Gy) should still be possible.**

## 10. ADVERSE EVENTS

### 10.1 Definitions

#### 10.1.1 Adverse Event

According to GCP, an adverse event (AE) is defined as follows: Any untoward medical occurrence in a subject administered a pharmaceutical product and which does not necessarily have a causal relationship with this treatment. An AE can therefore be any unfavourable and unintended sign (including an abnormal laboratory finding), symptom, or disease temporally associated with the use of a medicinal (investigational) product, whether or not related to the medicinal (investigational) product.

An AE may be:

- New symptoms/ medical conditions
- New diagnosis
- Changes of laboratory parameters

The criteria that should be considered when determining whether an abnormal test finding should be reported as adverse event are as follows:

- Test result is associated with accompanying symptoms, and/or
- Test result require diagnostic testing or medical/surgical intervention, and/or
- Test result lead to a change in trial dosing outside the protocol-stipulated dose adjustments, or discontinuation from the trial, significant additional concomitant drug treatment, or other therapy, and/or
- Test result is considered clinically relevant at the discretion of the investigator or sponsor
- Intercurrent diseases and accidents
- Worsening of medical conditions/ diseases existing before clinical trial start
- Recurrence of disease
- Increase of frequency or intensity of episodic diseases.

A pre-existing disease or symptom will not be considered an adverse event unless there will be an untoward change in its intensity, frequency or quality. This change will be documented by an investigator.

Surgical procedures themselves are not AEs; they are therapeutic measures for conditions that require surgery. The condition for which the surgery is required may be an AE. Planned surgical measures permitted by the clinical trial protocol and the condition(s) leading to these measures are not AEs, if the condition leading to the measure was present prior to inclusion into the trial. In the latter case the condition should be reported as medical history.

AEs are classified as "non-serious" or "serious".

### 10.1.2 Serious Adverse Event, SAE

A serious adverse event (SAE) is an AE that regardless of the dosage of the IMP (GAZYVARO) or by irradiation:

- Results in death
- Is life-threatening (the term life-threatening refers to an event in which the subject was at risk of death at the time of event and not to an event which hypothetically might have caused death if it was more severe)
- Requires hospitalisation or prolongation of existing hospitalisation\*
- Results in persistent or significant disability/ incapacity\*\*
- Is a congenital anomaly/ birth defect or
- Is otherwise medically relevant

\* Hospitalisation for performing protocol-required procedures or administration of study treatment is not classified as an SAE. Hospitalisations for disease-related procedures (surgery, imaging, laboratory tests) or any procedures planned before entry into the study are not considered SAEs. Hospitalisations for social reasons in the absence of an adverse event are not classified as SAEs either.

\*\* Persistent or significant disability or incapacity means that there is a substantial disruption of a person's ability to carry out normal life functions. The irreversible injury of an organ function (e.g. paresis, diabetes, cardiac arrhythmia) fulfils this criterion.

Medical and scientific judgement should be exercised in deciding whether expedited reporting is appropriate in other situations - such as important medical events that may not be immediately life threatening or result in death or hospitalisation but may jeopardise the patient or may require intervention to prevent one of the other outcomes listed above. These should also usually be considered serious (examples of such events are intensive treatment in an emergency room or at home for allergic bronchospasm; blood dyscrasias or convulsions that do not result in hospitalisation; or development of drug dependency or drug abuse).

Progression of the malignancy under treatment needs not to be reported as an adverse event.

### 10.1.3 Serious Adverse Reaction, SAR

SAEs that potentially may be attributed to the investigational medicinal product (IMP; Gazyvaro) are to be classified as Serious Adverse Reactions (SARs). This terminology is also used in the context of side effects due to irradiation.

### 10.1.4 Expectedness

An 'unexpected' adverse reaction is one the nature or severity of which is not consistent with the applicable product information, the Investigator's Brochure (IB). Furthermore, reports, which add significant information on specificity or severity of a known adverse reaction constitute 'unexpected' events.

### 10.1.5 Suspected Unexpected Serious Adverse Reaction, SUSAR

SAEs that are both 'suspected', i.e., possibly related to the study drug (investigational medicinal product (IMP)) and 'unexpected', i.e., the nature and/ or severity of which is not consistent with the applicable product information are to be classified as Suspected Unexpected Serious Adverse Reactions (SUSARs).

In case, either the investigator who primary reported the SAE or the second assessor, classifies the SAE as 'suspected' and the SAE is unexpected it will be categorised as a SUSAR.

All SUSARs are subject to an expedited reporting to the responsible ethics committee(s), the competent authority and to all participating investigators

#### 10.1.6 AEs of special interest

The following AEs of special interest (AESI) will be reported as AE and SAE, considered an "Important Medical Event" even if no other criteria for seriousness apply, on the appropriate pages of the CRF and in the source documents:

- Non-drug specific Drug induced liver injury (DILI)

The drug causes hepatocellular injury, generally shown by more frequent 3-fold or greater elevations above the upper limits of normal (ULN) of ALT or AST than the (nonhepatotoxic) control agent or placebo. Among subjects showing such aminotransferase (AT) elevations, often with ATs much greater than 3 x ULN, some subjects also show elevation of serum total bilirubin (TBL) to  $\geq 2$  x ULN, without initial findings of cholestasis (serum alkaline phosphatase (ALP) activity  $< 2$  x ULN). No other reason can be found to explain the combination of increased AT and serum TBL, such as viral hepatitis A, B, or C, preexisting or acute liver disease, or another drug capable of causing the observed injury.)

- Progressive multifocal leucoencephalopathy (PML)

PML is a disease that is always serious, and that is fatal or severely debilitating in the large majority of patients. There is a potential risk that B-cell depletion may have an impact on the incidence and severity of infections. Rituximab has been associated with serious viral infections including PML. As obinutuzumab is more potent in terms of B-cell depletion than rituximab, there may be an increased risk of infections with obinutuzumab compared to rituximab. PML occurs almost exclusively in immunocompromised patients with deficits in the humoral or cellular immune response or both. PML has been observed most frequently in subjects with hematological malignancies (e.g. NHL and CLL) as well as subjects with liver transplants and autoimmune disease (e.g. SLE) [66].

- Suspected transmission of an infectious agent (STIAMP)

The definition of STIAMP is any organism, virus or infectious particle (e.g. prion protein transmitting Transmissible Spongiform Encephalopathy), pathogenic or non-pathogenic, is considered an infectious agent. A transmission of an infectious agent may be suspected from clinical symptoms or laboratory findings indicating an infection in a patient exposed to a medicinal product. As in the case of suspected adverse reactions and adverse reactions, the terms suspected transmission and transmission are considered synonymous. Confirmation of contamination (including inadequate inactivation/attenuation of infectious agents as active substances) of the concerned medicinal product increases the evidence for transmission of an infectious agent.

- Tumour-lysis syndrome (TLS)

Tumor lysis syndrome (TLS) is a well-known constellation of metabolic abnormalities resulting from spontaneous or treatment-related tumor necrosis or fulminant apoptosis. The metabolic abnormalities include: hyperkalemia, hyperuricemia and hyperphosphatemia with secondary hypocalcaemia with risk of renal failure. TLS has been reported in patients receiving anti-CD20 antibody therapy plus chemotherapy.

The presence of known risk factors such as bulky disease, preexisting (moderate) renal insufficiency, high ALC and high uric acid levels (> 8 mg/dL) prior to therapy are known to increase the likelihood of TLS. Early identification of patients at risk and the prevention of TLS development with the initiation of preventive measures, as well as the careful monitoring for early signs of laboratory TLS and the prompt initiation of supportive care are critical to prevent potentially life-threatening metabolic derangements [64].

All AESIs will be entered into the pharmacovigilance database. However, if none of the ‘seriousness’ criteria applies, the AESIs are not to be handled as serious adverse events. Hence, even if they are ‘unexpected’ and potentially related to the IMP, they will not undergo expedited reporting.

